#### 10.2.4 RBT and LPV Quantitation

RBT and LPV concentrations will be determined in an ACTG CLIA-certified pharmacology laboratory. The goal is for RBT and LPV concentration information from the day  $12 \pm 2$  PK study to be available for evaluation by the A5290 core team during the dose-finding period in accrual period 1 participants. Accrual period 1 participants for whom early dose adjustments are recommended will have drug concentrations repeated  $12 \pm 2$  days after initiating the adjusted dose. If no early PK or safety trends are identified during core team or SMC monitoring, dosing will continue in participants enrolled during accrual period 1 as per assigned treatment arm.

10.3 Primary and Secondary Data, Modeling, and Data Analysis for the Dose-Finding Study in Accrual Period 1 Participants

The observed concentrations of RBT and LPV and the times post dose that these concentrations were obtained will be summarized.

The primary PK characteristics for RBT are:  $C_{max}$ , time to maximum plasma concentration ( $T_{max}$ ), 24-hour post dose plasma concentration ( $C_{24h}$ ), area under the concentration-time curve ( $AUC_{0-24}$ ), and apparent oral clearance (CL/F). Standard noncompartmental techniques will be used to assess PK parameters. The AUC will be determined using the trapezoidal rule.  $C_{max}$  will be taken as the maximum observed concentration.  $T_{max}$  is the time at which  $C_{max}$  occurs. If more than one  $C_{max}$  and  $T_{max}$  occur in a given profile, the median of these values will be taken. The 24-hour post dose concentrations will be the directly measured value. Apparent oral clearance will be calculated as  $CL/F = \text{dose}/AUC_{0-24}$ . The elimination half-life is considered a secondary parameter and will be determined using regression analysis when possible.

The primary PK characteristics for LPV are:  $C_{max}$ ,  $T_{max}$ ,  $C_{12h}$ ,  $AUC_{0-12}$ , and CL/F. Standard noncompartmental techniques will be used to assess PK parameters. The AUC will be determined using the trapezoidal rule.  $C_{max}$  will be taken as the maximum observed concentration.  $T_{max}$  is the time at which  $C_{max}$  occurs. If more than one  $C_{max}$  and  $T_{max}$  occur in a given profile, the median of these values will be taken. The pre-dose concentration will be taken as the 12-hour post dose concentration, and will be the directly measured value. CL/F will be calculated as  $CL/F = \text{dose}/AUC_{0-12}$ . The elimination half-life is considered a secondary parameter and will be determined using regression analysis when possible.

For RBT (Arms A and C), an equivalence approach will be used to compare RBT AUC and  $C_{max}$  with those of two control datasets from previous PK studies, as described below. This approach will evaluate whether the 90% CIs of the ratios of the RBT + LPV/r relative to daily RBT PK characteristics are fully contained within a specified no effect boundary. A no effect range of 0.67 to 1.50 will be used. Arms A and C will be judged to pass the RBT PK criterion if equivalence is declared.

For LPV in Arm B, the primary PK parameter is the  $C_{min}$  (trough or 12-hour post dose concentration), and the acceptable lower value is  $\geq 1 \text{ mg/L}$ . Arm B will be judged to pass the LPV  $C_{min}$  criterion if no more than three participants have a  $C_{min} < 1 \text{ mg/L}$ .

RBT pharmacokinetics will be evaluated in Arms A and C of A5290 to investigate the question of whether a RBT dose of 150 mg once daily is adequate when given with LPV/r. An equivalence approach will be used to compare the RBT AUC and  $C_{max}$  with those of two historical controls. For this comparison, we have selected a recent publication describing a drug-drug interaction study of darunavir/ritonavir and RBT. In this healthy volunteer study, one arm contained RBT only given for 12 days at a dose of 300 mg once daily. The strength of this control dataset is the 300 mg RBT dose and an intensive pharmacokinetic study. The recommended dose reduction strategy for RBT to 150 mg once daily when given with a ritonavir-boosted PI is intended to approximate the exposure of the standard, 300 mg once daily dose. Thus, this selected control dataset provides the appropriate comparison for the 150 mg once daily dose of RBT in A5290.

and the necessary PK data. A second control dataset will also be examined. Some RBT PK data are now beginning to become available from studies conducted in HIV- and TB-infected persons. One study is that of Naiker, et al. This study is another good comparison for A5290 because of similarities in patients, drugs and dosing regimens. However, because this study is only available in abstract form, has a limited sample size (n=16), and the majority of the available RBT PK data are from studies conducted in healthy volunteers, this study will not be used as the sole, control dataset but will be used as a supplementary control to the data from the darunavir/ritonavir and RBT PK study previously described.

#### 10.4 Anticipated Outcomes for the Dose-Finding Study in Accrual Period 1 Participants

These data will provide guidance to the A5290 core team and SMC prior to the opening of accrual period 2 as to whether the current management approach for the drug-drug interaction between RBT and LPV/r (a RBT dose of 150 mg once daily) produces RBT plasma concentrations comparable to those of RBT 300 mg once daily without LPV/r observed in prior PK studies. Additionally, these accrual period 1 PK evaluations will provide guidance as to whether the management strategy for the drug-drug interaction between LPV/r and RIF (Arm B) of using double-dose LPV/r (i.e., 800/200 mg BID) achieves adequate LPV concentrations.

If the RBT PK data fall outside the effective ranges and the team determines that a dose adjustment is warranted, the team will consider two possibilities – an adjustment to 300 mg TIW as indicated in Table 5.1 or a change to 300 mg daily based on the RBT PK from the accrual period 1 dose-finding period and the assessment of which dose adjustment would best approximate the reference PK parameters for RBT 300 mg once daily given without LPV/r, as described above in section 10.3. If the team determines a RBT dose decrease is warranted, the dose will be reduced to the 150 mg TIW dose currently recommended. No substantive effect of RBT on LPV/r concentrations is expected based on prior PK data with this combination; however, if levels in the ranges noted for Arm B are observed in Arm A or Arm C, then dose adjustments will be the same as for Arm B.

#### 10.5 Population Pharmacokinetic Study Design in Participants Enrolled During Accrual Period 2

##### 10.5.1 Sample Size for Accrual Period 2

411 participants will be randomized 1:1:1 to Arm A, B, or C (or with equal probability to the remaining sample size in the remaining treatment arms) at the doses determined during the dose-finding period in accrual period 1 participants, and with a population PK approach in the accrual period 2.

##### 10.5.2 Sampling Strategy – Specimen Collection

Blood samples for population PK studies will be collected at the week 2 and week 8 clinic visits. Two blood samples, if possible, will be collected at each of these clinic visits. These sampling strategies apply to all three arms of A5290.

Plasma will be frozen and periodically batch shipped to the ACTG repository, which will re-ship them to designated ACTG PSL. Refer to the A5290 LPC for additional instructions.

At week 2, the priority blood sample should be collected within a window of 6-12 hours after administration of a dose of LPV/r. This dose of LPV/r may be either the evening dose the day before the clinic visit or the morning dose the day of the clinic visit. The second blood sample may be collected at any time before or after this sample, as long as there is at least a 2-hour interval between sample collections.

At week 8, the first and priority blood sample should be collected within a window of 2 to 4 hours after administration of RBT. A second blood sample may be collected at any time after this blood sample, as long as there is at least a 2-hour interval between sample collections.

For participants in Arm C, samples obtained from this sampling schedule at weeks 2 and 8 will also be suitable for RAL.

#### 10.5.3 Medication Adherence

All participants should be counseled to ensure strict compliance with their TB and HIV medications. Participants should be queried as to the number of doses of TB and HIV medications not taken in the previous 3 days, and this number should be recorded on the CRF. The time and date of all doses of all TB and HIV medications taken the day prior to the PK study day (i.e., weeks 2 and 8) must be recorded on the CRF. The time of all doses of TB and HIV medications given on the day of the PK study should be recorded on the CRF. The PK study should not be performed if participants report missing any doses of any TB or HIV medication on the day prior to the PK study. If this situation occurs, the participant should be counseled about medication adherence, and a repeat PK study may be performed  $\geq$  5 days later, and no more than 12 days later than the originally scheduled PK study. If on this second PK day, the same participant should report missing any doses on the day prior to the PK study, the PK study should not be performed and this individual will not be considered eligible for the PK study.

#### 10.5.4 RBT, LPV, and RAL Quantitation

RBT, LPV, and RAL concentrations will be determined in an ACTG CLIA-certified pharmacology laboratory.

### 10.6 Primary and Secondary Data, Modeling, and Data Analysis for the Population PK Study in Accrual Period 2 Participants

For this analysis, the primary interest will be the PK characteristics of RBT and LPV; the PK characteristics of RAL are a secondary objective. PK characteristics will be evaluated using NONMEM version VI (GloboMax, Hanover, MD). NONMEM uses mixed effects

(random and fixed) regression to estimate population means and variances of PK parameters and identify factors, such as body weight, gender or concomitant drug that may influence these parameters. Base models will be developed using first-order conditional estimation with interaction. A stepwise procedure will be used to determine whether a one- or two-compartment model best fits the plasma data under the principle of parsimony. An exponential error distribution will be assumed for the description of both interpatient and intrapatient (residual) PK parameter variability. Residual error will be modeled as an additive plus proportional error model. If necessary, poorly identified structural parameters, such as the absorption rate constant, may be fixed to usual adult values. The following covariates will be collected at baseline or during follow-up visits: sex, age, weight, race, markers of renal function (estimate creatinine clearance), HIV regimen (e.g., Arm A, B, or C) and HIV response markers, and TB regimen and response markers. The influence of each covariate on the PK characteristics of RBT and LPV will be tested sequentially. At each step, the goodness of fit plots will also be evaluated.

At the end of the analysis, all covariates that show an influence on the parameters will be evaluated again by comparison of the full model (with all factors included) with a model from which each of the factors is deleted sequentially. For forward addition and backward elimination a decrease in objective function value by 3.84 ( $p \leq 0.05$ ) and 6.64 ( $p \leq 0.01$ ), respectively, would advocate sufficiently influential covariates. NONMEM uses extended least squares to calculate the objective function and the difference in the value of the objective function between models is approximately chi-squared distributed. A difference in objective function of greater than 6.6 is considered significant (6.6 corresponds to a chi-square for  $p=0.01$  with 1 degree of freedom) when one parameter is added or the covariate (e.g., body weight) is replaced. This is analogous to the commonly used F test to select among regression models. The primary outcome of this analysis is to identify the model that best describes the plasma PK of RBT, LPV, and RAL and to investigate whether any of the covariates influence the PK of these ART and TB agents. The final model will include all significant covariates (if any) and the parameter estimates for all parameters together with the estimates of residual and interpatient variability. The accuracy and robustness of the final population model will be assessed using a bootstrap method. A secondary objective of this combined analysis will be to develop a linked population PK-PD model in NONMEM to evaluate potential relationships between these plasma concentrations/PK characteristics and therapeutic outcomes (i.e., response to HIV therapy and to TB treatment, and adverse events).

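### Protocol section 10.6 lets on-treatment HIV and TB response markers into the population PK model whose exposures are then related to those same responses

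*Protocol*

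**What the plan says.** Protocol section 10.6 sets out the population PK analysis for accrual period 2. On candidate covariates it says "The following covariates will be collected at baseline or during follow-up visits". After sex, age, weight, race and renal function, the list ends with "HIV regimen (e.g., Arm A, B, or C) and HIV response markers, and TB regimen and response markers". The individual markers are not named. All listed items enter the search: "The influence of each covariate on the PK characteristics of RBT and LPV will be tested sequentially".

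Selection is by change in the NONMEM objective function, with 3.84 for forward addition and 6.64 for backward elimination. On retention, the section states "The final model will include all significant covariates (if any", with no exception for response markers.

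A secondary objective of the same combined analysis is "to develop a linked population PK-PD model in NONMEM to evaluate potential relationships between these plasma concentrations/PK characteristics and therapeutic outcomes". The outcomes listed there are HIV response, TB response and adverse events. Section 10.7 repeats the exposure-response aim and gives rifabutin thresholds for TB outcome as an example. Secondary objective 1.3.1 includes the association of rifamycin exposure with TB outcome.

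No section confines the markers to baseline, removes them before the PK-PD step, or asks for a PK model without them.

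**The concern.** Response may be used to predict exposure in the first step, and exposure is used to explain response in the second. With rich sampling this would matter little, because each person's own concentrations would fix the estimate. Section 10.5.2 allows two samples, if possible, at each of weeks 2 and 8, so at most four per person. With so few, an individual estimate is pulled toward the value the model predicts for people with the same covariates. If response is one of those covariates, responders are pulled toward the responder mean and non-responders toward the non-responder mean. Part of the gap between the groups is then put there by the model.

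At stake are the size of the exposure-response slope and the apparent strength of evidence for it. A claim about an adequate rifabutin concentration would lean on both. The bootstrap planned in 10.6 would not reveal the problem, because every resample repeats the same structure.

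**Working it through.** **The plan's own figures.** The chi-square quantiles with 1 df are 3.841 at p = 0.05 and 6.635 at p = 0.01, so the stated 3.84 and 6.64 (6.6) reproduce.

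**Inputs from the documents.** Accrual period 2 has 411 participants (10.5.1). Rifabutin is given in two of three equal arms, so 411 × 2/3 = 274. A covariate is taken as retained when the objective function falls by at least 6.64.

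**Assumptions.** The documents give no shrinkage and no exposure-response effect. Shrinkage s (variance scale) is varied from 10% to 50%. The PK-PD step is taken to regress response on individual exposure estimates.

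**Formula.** Let X be true log-exposure and Y response, both standardized, with correlation ρ. Let W be the sparse-sample information on X, with reliability L = 1 − s.

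- Marker not in the PK model: the estimate is L·W. Its covariance with Y is Lρ and its variance is L² × (1/L) = L. The slope is Lρ/L = ρ, which is correct.
- Marker in the PK model: the estimate is ρY + L′(W − ρY), with L′ = (1 − ρ²)/[(1 − ρ²) + (1 − L)/L]. Its covariance with Y is ρ and its variance is ρ² + L′(1 − ρ²). The slope is ρ/[ρ² + L′(1 − ρ²)], close to ρ/L for small ρ.

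Example with s = 0.30 and ρ = 0.20: (1 − L)/L = 0.4286; L′ = 0.96/1.3886 = 0.6914; variance = 0.04 + 0.6914 × 0.96 = 0.7037; inflation = 1/0.7037 = 1.42. The approximation gives 1/0.70 = 1.43.

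| Assumed shrinkage | Slope inflation if marker retained (ρ = 0.20) | 1/(1 − s) |
|---|---|---|
| 10% | 1.11 | 1.11 |
| 20% | 1.25 | 1.25 |
| 30% | 1.42 | 1.43 |
| 40% | 1.65 | 1.67 |
| 50% | 1.96 | 2.00 |

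**Averaging over retention, continuous response.** In 20,000 simulated trials with true slope 0.20 and 30% shrinkage, 274 participants gave retention in 59% of runs and a mean slope of 0.263, against 0.200 without the marker. With 411 participants, retention was 80% and the means were 0.276 and 0.200.

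**Averaging over retention, binary response.** The setting was 274 participants, 70% responders, log-exposure SD 0.32, a difference of 0.10 in mean log-exposure (true log-odds slope 0.10/0.32² = 0.98) and 40% shrinkage. The marker was retained in about 23% of runs. The mean slope over all runs was about 1.3 with the planned procedure and 1.0 without the marker. Detection at p < 0.05 was the same both ways, at about 45%.

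**No true relation.** The marker was retained in about 1% of runs. The false-positive rate at 0.05 was about 5% either way. At 0.001 it rose from about 0.1% to about 1% for shrinkage of 20% or more. At 10% shrinkage it rose only from 0.09% to 0.27% (n = 274). The reason is simple: a marker kept at p ≤ 0.01 comes from a run already significant at 0.05, so only the depth of the p-value changes. The retention rate caps the excess at 0.001.

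**The case against.** Several points on the other side stand.

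- **The analysis may never be run.** Section 10.6 is written for accrual period 2. SAP section 1.6 says that period will not open (although the overview in SAP 1.3 still describes it opening). SAP section 5.2 addresses the PK objectives with summaries and Wilcoxon tests, and the SAP describes no covariate search or PK-PD model. This limits the practical effect but does not correct the protocol text.
- **It is exploratory.** Protocol 9.2.4 places the accrual period 2 concentrations among supportive analyses to be detailed in separate plans. Those plans could close the gap.
- **The markers are unnamed.** Baseline CD4 count or HIV RNA would not be circular. A reader might infer that the week-48 result or TB outcome is itself a planned covariate. The text permits on-treatment markers but does not say that.
- **The PK-PD method is open.** Section 10.6 does not say whether the linked model is fitted in sequence or jointly, and it mentions plasma concentrations as well as PK characteristics. Observed concentrations are not shrunken, so the inflation applies only if exposures from the model are used.

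Two stronger readings should be resisted. In the binary simulation, runs that kept the marker had a mean slope near 3 against a true 0.98, and a reader might blame circularity for all of it. In those same runs the slope was already about 1.7 with no marker in the model, because they were selected for significance. A reader might also infer that the cut-offs are wrong. The text ties 6.6 to one added parameter with 1 df, and for rifabutin arm has only two levels. What remains is a minor note: if arm is tested as a three-level factor for lopinavir, 3.84 and 6.64 correspond to 14.7% and 3.6% on 2 df.

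**Conclusion.** The point holds as a conditional weakness in the protocol text. Section 10.6 permits an on-treatment response marker to shape the exposure estimates that are then used to explain response. If one is retained and those estimates are used, the slope is exaggerated by about 1/(1 − shrinkage), or 1.1 to 2 times over an assumed 10–50%. Averaged over all runs with 274 participants and 40% shrinkage, the excess is about 30%. These sizes rest on assumed shrinkage and effect, and on a two-stage regression; the direction does not depend on the particular values.

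A reader might infer that false positives are inflated or that the trial's main conclusions are at risk. Neither follows: the 5% error rate is unchanged, and the week-48 virologic comparison does not use this model. Because the SAP says accrual period 2 will not open, the effect on this trial's own results is small. The point applies to any population PK-PD analysis that follows 10.6.

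**What to change.** In section 10.6, or in the separate PK analysis plan, make one of two changes:

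1. Limit PK-model covariates to baseline and non-outcome measures: sex, age, weight, race, creatinine clearance, arm, and baseline CD4 count and HIV RNA. Response then meets exposure only in the PK-PD step.
2. Keep the wider search, but take the exposures for the PK-PD step from a model without on-treatment response markers.

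Under either option, if the team thinks recovery from HIV or TB alters PK, it can examine and report that separately. As a minor addition, state that multi-level covariates use df-specific cut-offs (5.99 and 9.21 for 2 df), which matters only if the three-level arm factor is tested for lopinavir.

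The cost is a few lines of text and, under the second option, one further model fit. No new data are needed.

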#### 10.7 Anticipated Outcomes in the Population PK Study in Accrual Period 2 Participants

These population PK studies will provide data on whether the PK basis for the selection of the RBT and LPV dosing strategies during the dose-finding period in accrual period 1 participants can be confirmed in a much larger population of participants enrolled during accrual period 2. Additionally, these population PK data will provide information on the concentrations of RAL for participants in Arm C. The PK data for RBT, LPV, and RAL will be used to investigate exposure-response relationships among RBT, LPV, and RAL and measures of response to HIV therapy and TB therapy, and these data may fill gaps in our knowledge, for example, of whether threshold concentrations of RBT are associated with positive or negative (e.g., acquired rifamycin resistance) TB treatment outcomes.

**11.0 DATA COLLECTION AND MONITORING AND ADVERSE EVENT REPORTING****11.1 Records to Be Kept**

Case report forms (CRF) will be provided for each participant. Participants must not be identified by name on any CRFs. Participants will be identified by the patient identification number (PID) and study identification number (SID) provided by the ACTG DMC upon randomization.

**11.2 Role of Data Management**

11.2.1 Instructions concerning the recording of study data on CRFs will be provided by the ACTG DMC. Each CRS is responsible for keying the data in a timely fashion.

11.2.2 It is the responsibility of the ACTG DMC to assure the quality of computerized data for each ACTG study. This role extends from protocol development to generation of the final study databases.

**11.3 Clinical Site Monitoring and Record Availability**

11.3.1 Site monitors under contract to the NIAID will visit participating clinical research sites to review the individual participant records, including consent forms, CRFs, supporting data, laboratory specimen records, and medical records (physicians' progress notes, nurses' notes, individuals' hospital charts), to ensure protection of study participants, compliance with the protocol, and accuracy and completeness of records. The monitors also will inspect sites' regulatory files to ensure that regulatory requirements are being followed and sites' pharmacies to review product storage and management.

11.3.2 The site investigator will make study documents (e.g., consent forms, drug distribution forms, CRFs) and pertinent hospital or clinic records readily available for inspection by the local IRB/EC, the site monitors, the US FDA, the NIAID, the OHRP, the local governmental authorities, and the pharmaceutical supporter(s) or designee for confirmation of the study data.

